### 6.2 Secondary objective

1. To study the effects of oral cladribine on:
  - a. CSF OCBs and free immunoglobulin kappa and lambda light chain levels (FLC).
  - b. CSF markers of inflammation, in particular CXCL-13 and urine markers of inflammation (neopterin).
  - c. CSF markers of neuroaxonal damage, in particular free neurofilament light chains.
  - d. On the peripheral repertoire B-cells (immunoglobulin) and T-cells (T cell receptor) and plasma cells (soluble receptors).
2. To compare CSF OCB positivity and CSF light chain levels with a contemporary control group of alemtuzumab treated pwMS (historical data).

### 6.3 Tertiary objective

1. To compare B and T cell repertoire with a contemporary control group of alemtuzumab treated pwMS (historical data).
2. To evaluate the effect of changes in the immune cell profile on clinical measures of disability, MRI activity and PROMS.

### 6.4 Primary endpoint

The time course of B, plasmablast and T cell depletion and re-population over 96w to see if any particular population of cells is more susceptible to cladribine, i.e. memory B-cells (CD19+/CD27+). These changes will be compared to populations of naïve B cells.

### 6.5 Secondary endpoint

1. a. Relative change in CSF OCB pre- and post-cladribine (baseline vs 48w and 96w).
- b. Relative change in CSF cytokines and chemokines (baseline vs 48 w and 96w period), in particular CXCL-13 pre- and post-cladribine and urine neopterin levels.
- c. Relative change in CSF neurofilament light chain pre-and post-cladribine (baseline vs 48w and 96w).
- d. Relative change in blood immunoglobulin levels and T cell receptor levels (baseline vs 48 w and 96w period) pre-and post-cladribine and urine immunoglobulin levels.
2. Relative change in CSF soluble CD138 (plasma cell marker) pre- and post-cladribine (baseline vs. 48w and 96w).
3. Occurrence of CSF OCB positivity and relative change in CSF FLC post-cladribine *versus* historical data post-alemtuzumab (baseline vs. 48w and 96w).

### 6.6 Tertiary endpoint

1. Relative change in B and T cell repertoire post-cladribine *versus* historical data post-alemtuzumab.
2. Correlation between baseline, 48w and 96w immune cell profiles and baseline, 48w and 96w EDSS, MSFC, T2 lesion load and gadolinium enhancement, MSIS-29 and their changes.

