	
 
• Patients must be willing and able to undergo lumbar punctures
 
• Patients who are OCB positive in their CSF (from previous diagnostic lumbar puncture)
 
 
Exclusion:
 
 
• Ineligible for oral cladribine under NHS England prescribing guidelines and those participating in MAGNIFY-MS study (cladribine tablets in active MS)
 
• Unsuitable to have a lumbar puncture (e.g. spinal deformity, tethered cord syndrome, or the use of aspirin or anticoagulants), and those unable to comply with study requirements, including frequency of visits and lumbar punctures
 
• Presence of comorbidities in which administration of cladribine is contraindicated
 
• Abnormal baseline investigations (WCC<3 x 10^9/l, neutrophil count < 1.5 x 10^9/l, platelet count < 100 x 10^9/l, haemoglobin < 110 g/l, LFT >/= 3x upper limit of normal site reference ranges, potassium < 2.8 mmol/l or > 5.5 mmol/l, sodium < 125 mmol/l, creatinine > 130 umol/l
 

Statistical methodology and analysis (if applicable)	
Changes in total immune cell counts will be analysed using descriptive statistics, including reduction relative to baseline and absolute reduction in numbers. Time to nadir and recovery will be done using best-fit modelling.
 
Total blood IgG and free kappa and lambda light chain levels will be normalised to albumin levels. McNemar's test will be used to compare differences in OCB status between baseline, year one or year two. The association between different biomarkers, clinical and imaging parameters will be analysed using multiple regression.

Study duration	96 weeks.

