observation was not confirmed in a larger, more definitive, German study (Harrer et al. 2013). It is important to note that in pwMS treated with alemtuzumab intrathecal oligoclonal bands persist (Hill-Cawthorne et al. 2012). In comparison, in the Scripps chronic progressive cladribine trial, patients treated with cladribine had a significant decline in the number of oligoclonal bands (Sipe et al. 1994). Although the OCBs did not disappear this study used agarose gel electrophoresis, a technique that is not specific for detecting immunoglobulins and is now obsolete (Freedman et al. 2005).

We hypothesise that it will be important to target intrathecal plasma cells therapeutically to delay the onset, or slow down, the clinically-apparent progressive phase of MS. Most licensed DMTs are effective, to a greater or lesser extent, at suppressing relapses and focal MRI activity (new T2 or Gd-enhancing lesions), however, none of the treatments have yet been shown to prevent the onset of non-relapsing progressive disease. Why? If the non-relapsing progressive phase of the disease is driven by intrathecal OCBs, the resistance of long-lived plasma cells to current therapeutic intervention may explain why this phase of the disease is so resistant to treatment. To successfully treat, or prevent, progressive MS intrathecal plasma cells may need to be eliminated to prevent antibody mediated mechanisms that underlie the progressive phase of MS. We are thus actively exploring treatments that target intrathecal plasma cells; for example, we are proposing that cladribine (2-chlorodeoxyadenosine) a nucleoside analogue penetrates the blood-brain barrier (BBB) and has been shown to have biological activity against myeloma cells, or malignant plasma cells, albeit in combination with a STAT3 inhibitor (Ma et al. 2011).

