## 8. Study design

Patients will be required to give consent for 15mL of peripheral venous blood (plasma and serum), urine and CSF to be collected at multiple time points over 96 weeks. These samples will be collected in addition to those collected for routine clinical monitoring. They will be informed that their decision to consent for their blood products to be used in research will have no impact on their current or future treatment, and it should not affect their decision to start, continue or discontinue their MS therapy.

Venous blood samples will be analysed by flow cytometry. B cell populations will be determined using specific markers for B cell populations including CD10, CD19, CD25, CD27, CD38 and IgD. This will allow the analysis of the number of memory B cells (CD19+/CD27+), memory B cell subsets (CD19+/CD27+/IgD-/+ and CD19+/CD27+/CD25-/+) and plasmablasts (CD19+/CD27+/CD38+) in the subject's blood samples. As controls, naive B cells CD19+/CD27 and T cells (CD19

/CD3+/CD4+/CD8+) will also be examined. Whole blood for DNA extraction will be collected and stored for deep sequencing to analyse the B and T cell repertoire using Adaptive Biotechnologies' immunoSEQ technology; these assays can identify millions of T- and B-cell receptors in a single sample. Using this technology will allow us to compare the impact of cladribine on the adaptive immune system over time and to compare it with similar data from alemtuzumab treated subjects from [name] laboratory in Munster.

CSF will be collected using an atraumatic needle. CSF will be processed for routine biochemistry and aliquots will be stored for OCBs, FLC, B cells: soluble CD19 and plasma cells: soluble CD138; inflammatory markers: urine neopterin and multiplex cytokine profile; and neurodegenerative markers: NF, GFAP, NCAM, GAP-43 and S100B levels.

Study subjects will also be examined annually, have a routine annual MRI T2 lesion load and gadolinium enhancement, and the following outcome measures assessed EDSS, 9-HPT, T25FW, MSIS-29 and other routine clinical outcome measures at 24 weekly intervals.

Historical control data from 12 post-alemtuzumab treated subjects (Barts Health) for secondary endpoints (CSF OCB & FLC) and tertiary endpoints (B and T cell repertoires) will be used as comparators.

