## 11.2 Method of analysis

Depletion and re-population kinetics of B and T cell subsets will be analysed using descriptive statistics. An interim analysis of the year 1 data is planned, and a further analysis of the whole data will be performed at the end of the study. These will be calculated as a reduction relative to baseline counts and the absolute reduction in numbers. Time to nadir and recovery will be done using best-fit modelling. Categorical data based on absolute cut-offs will be presented as proportions, e.g. for absolute lymphocyte counts this will use the WHO boundaries.

Total blood IgG and free kappa and lambda light chain levels will be normalised to albumin levels. McNemar's test will be used to compare differences in OCB status between baseline and year one CSF or year two CSF. Differences in CSF and blood biomarkers, clinical and imaging parameters between baseline and 48w and 96w will be analysed using multiple regression. A detailed SAP will be prepared and approved during the recruitment period well before data becomes available.

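### Tertiary endpoint 2 names no count of new or enlarging T2 lesions, so it captures on-treatment MRI activity incompletely (minor)

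*Combined protocol and SAP*

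**What the plan says.** Section 6.3, item 2 sets the aim: "To evaluate the effect of changes in the immune cell profile on clinical measures of disability, MRI activity and PROMS".

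Section 6.6, item 2 turns this into "Correlation between baseline, 48w and 96w immune cell profiles and baseline, 48w and 96w EDSS, MSFC", and the list continues with "T2 lesion load and gadolinium enhancement, MSIS-29 and their changes". The MRI variables are therefore T2 lesion load and gadolinium enhancement at baseline, week 48 and week 96, plus the change in each.

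Section 8 gives the source of the data: subjects "have a routine annual MRI T2 lesion load and gadolinium enhancement". Scans are yearly and part of routine care.

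Section 5.1, on what licensed therapies suppress, writes "focal MRI activity (new T2 or Gd-enhancing lesions".

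On analysis, section 11.2 says that differences in biomarkers and in "clinical and imaging parameters between baseline and 48w and 96w will be analysed using multiple regression". The synopsis (section 4) says "The association between different biomarkers, clinical and imaging parameters will be analysed using multiple regression". Neither says how a scan is read or whether T2 load is a volume or a number. No count of new or enlarging T2 lesions appears in the endpoint, design or analysis sections.

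**The concern.** The objective is about activity: what the disease did on MRI while the cells were depleted and repopulating. The named variables approach that only indirectly.

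- **T2 load, level.** It adds up every lesion the patient has accumulated, so it mainly reflects the years before cladribine.
- **T2 load, change.** If load is a volume, the change is net, and a new lesion can be offset by shrinkage of an old one.
- **Gadolinium enhancement.** One reading a year shows only lesions that are enhancing on that day. A lesion that formed and stopped enhancing between scans is not seen.

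Comparing consecutive annual scans for new or enlarging T2 lesions would record activity over the whole interval, from images already planned. Without it, a weak association between cell depletion and MRI could arise partly because the outcome missed most of the activity.

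**Working it through.** **The plan's own figure.** The only sample-size calculation (section 11.1) is for loss of oligoclonal bands: 0% versus 50%, 80% power, 5% alpha. Taking a two-sided pooled comparison of two proportions:

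n = [1.960 × √(2 × 0.25 × 0.75) + 0.842 × √(0.5 × 0.5)]² / 0.5² = (1.200 + 0.421)² / 0.25 = 10.5, so 11 per group.

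This reproduces the stated 11. The stated 13 is 11 × 1.2 = 13.2 rounded down; 11/0.8 = 13.75 would give 14. The calculation says nothing about MRI and is used here only to set n at 11 to 13.

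**Assumptions (none is in the documents).** New lesions arise as a Poisson process at r = 0.25 to 1.0 per patient-year, with the same rate in all patients. Each enhances for w = 2 to 8 weeks and leaves a visible T2 lesion. The two on-treatment scans are independent.

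**Share of a 48-week interval seen by one gadolinium scan.** w/48: 2/48 = 4% to 8/48 = 17%.

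**Formulas for n = 11.**
- Expected gadolinium-positive patients at one scan: 11 × [1 − exp(−r·w/52)]
- Chance that all 11 are negative at one scan: exp(−11·r·w/52)
- Chance that all 22 readings over weeks 48 and 96 are negative: exp(−22·r·w/52)
- Expected patients with at least one new T2 lesion in 48 weeks: 11 × [1 − exp(−r·48/52)]

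| | r = 0.25, w = 2 | r = 0.5, w = 6 | r = 1.0, w = 8 |
|---|---|---|---|
| r·w/52 | 0.0096 | 0.0577 | 0.1538 |
| Expected Gd-positive, one scan | 0.1 | 0.6 | 1.6 |
| All 11 negative, one scan | 90% | 53% | 18% |
| All negative, both scans | 81% | 28% | 3% |
| Expected with a new T2 lesion, one interval | 2.3 | 4.1 | 6.6 |

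In the middle column, the chance that at most one patient is positive is about 88% for gadolinium at one scan and about 5% for new T2 lesions over the interval.

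**Check without the Poisson model.** Assume directly the proportion of patients who are positive and use the binomial distribution.

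| Assumed proportion positive | P(0 or 1 positive), n = 11 | n = 13 |
|---|---|---|
| 5% | 0.90 | 0.87 |
| 10% | 0.70 | 0.62 |
| 20% | 0.32 | 0.23 |
| 30% | 0.11 | 0.06 |
| 50% | 0.006 | 0.002 |

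Sparse gadolinium is thus a low-rate result: likely at 5%, unlikely at 20%. An interval T2 count with 30-50% of patients positive would rarely be this sparse.

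**Precision of any correlation.** At n = 11, two-sided p < 0.05 needs |r| = 2.262/√(9 + 2.262²) = 0.60, and 80% power needs a true correlation of tanh(2.80/√8) = 0.76. At n = 13 the figures are 0.55 and 0.71. These limits apply to every MRI variable, including the one proposed below.

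**The case against.** A reader might infer that the endpoint is blind to lesions formed on treatment, that it has almost no variation to correlate, and that the MRI part of the objective therefore cannot be answered. The documents do not support this.

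- Section 6.6 includes the changes in each variable, so lesions accrued on treatment enter through change in T2 load. Gadolinium at weeks 48 and 96 also detects some of them. The measures are incomplete, not blind.
- No variance or lesion rate for either measure appears anywhere. Sparsity applies at most to on-treatment gadolinium, and its range is wide. T2 load can vary freely between patients.
- The gadolinium correlation need not be undefined even if every on-treatment scan is negative, because change from baseline still varies if someone enhanced at baseline. In that case, however, the change carries only baseline information.
- T2 load is undefined. If it is a lesion number, its change comes close to a new-lesion count.
- Section 5.1 is background, not an endpoint definition, and gadolinium is one of the two elements it names.
- With 11 to 13 patients a null correlation would be uninformative whichever MRI measure is used, so it could not be blamed on the measure alone.
- The study is exploratory with descriptive analyses (section 11.1), and section 11.2 promises a detailed SAP before data become available.

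All of these stand, and they limit the point to an incomplete and partly undefined activity measure. They do not remove it: the new-lesion half of the protocol's own description of activity is not named, and T2 load is not defined.

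**Conclusion.** The point holds as a minor one. Tertiary endpoint 2 measures MRI activity by T2 lesion load, its change, and gadolinium on annual scans, and so captures activity during treatment incompletely. Under the assumed lesion rates and enhancement times, the chance that no patient among 11 shows enhancement is 18-90% at one scan and 3-81% over both, against 2.3-6.6 patients expected to have a new T2 lesion in each 48-week interval. These ranges rest wholly on assumed inputs. If lesion rates differ between patients, fewer patients would be positive on either measure. The remark that change in T2 load is net assumes that load is a volume.

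No primary or secondary conclusion is affected.

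**What to change.** In section 6.6 item 2 and section 8, and in the detailed SAP promised in section 11.2:

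1. Define the MRI activity variable as the number of new or enlarging T2 lesions at week 48 versus baseline and at week 96 versus week 48, combined with gadolinium-enhancing lesions so that no lesion is counted twice.
2. Report the number of patients with any such activity in each interval.
3. State whether T2 lesion load is a volume or a count, and keep it as a measure of burden.

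Settle this before the year 1 interim analysis described in section 11.2. The cost is a sentence or two of text and a little extra time to read consecutive scans side by side; no scan or visit is added. The condition is that routine scans are comparable enough for lesions to be matched, which should be checked first. The change improves what is measured but does not make the correlation precise.

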## 7. Study population

This longitudinal study over 96 weeks will examine peripheral venous blood samples, CSF and urine of pwMS with RRMS who are treated with oral cladribine tablets under the NHS in Barts Health. Only those able to give consent to participate in the study will be included.

### 7.1 Inclusion criteria

1. Patients with MS who are being treated with oral cladribine at Barts Health NHS Trust will be approached to participate in this study.
2. Patients must be willing and able to undergo lumbar punctures.
3. Patients who are OCB positive in their CSF (previous diagnostic lumbar puncture).

### 7.2 Exclusion criteria

1. Ineligible for oral cladribine under NHS England prescribing guidelines and those participating in MAGNIFY-MS study (cladribine tablets in active MS).
2. Unsuitable to have a lumbar puncture, for example spinal deformity, tethered cord syndrome or the use of aspirin or anticoagulants, and those unable to comply with study requirements, including frequency of visits and lumbar punctures.
3. Presence of comorbidities in which the administration of cladribine is contraindicated.
4. Abnormal baseline investigations (WBC<3 x 10^9/l, lymphocytes <1.0 x 10^9/l, neutrophil count <1.5 x 10^9/l, platelet count <100 x 10^9, haemoglobin <110g/l, LFT>/3x upper limit of normal of site reference ranges, potassium <2.8mmol/l or >5.5mmol/l, sodium <125 mmol/l, creatinine >130 umol/l).

## 8. Study design

Patients will be required to give consent for 15mL of peripheral venous blood (plasma and serum), urine and CSF to be collected at multiple time points over 96 weeks. These samples will be collected in addition to those collected for routine clinical monitoring. They will be informed that their decision to consent for their blood products to be used in research will have no impact on their current or future treatment, and it should not affect their decision to start, continue or discontinue their MS therapy.

Venous blood samples will be analysed by flow cytometry. B cell populations will be determined using specific markers for B cell populations including CD10, CD19, CD25, CD27, CD38 and IgD. This will allow the analysis of the number of memory B cells (CD19+/CD27+), memory B cell subsets (CD19+/CD27+/IgD-/+ and CD19+/CD27+/CD25-/+) and plasmablasts (CD19+/CD27+/CD38+) in the subject's blood samples. As controls, naive B cells CD19+/CD27 and T cells (CD19

/CD3+/CD4+/CD8+) will also be examined. Whole blood for DNA extraction will be collected and stored for deep sequencing to analyse the B and T cell repertoire using Adaptive Biotechnologies' immunoSEQ technology; these assays can identify millions of T- and B-cell receptors in a single sample. Using this technology will allow us to compare the impact of cladribine on the adaptive immune system over time and to compare it with similar data from alemtuzumab treated subjects from [name] laboratory in Munster.

CSF will be collected using an atraumatic needle. CSF will be processed for routine biochemistry and aliquots will be stored for OCBs, FLC, B cells: soluble CD19 and plasma cells: soluble CD138; inflammatory markers: urine neopterin and multiplex cytokine profile; and neurodegenerative markers: NF, GFAP, NCAM, GAP-43 and S100B levels.

Study subjects will also be examined annually, have a routine annual MRI T2 lesion load and gadolinium enhancement, and the following outcome measures assessed EDSS, 9-HPT, T25FW, MSIS-29 and other routine clinical outcome measures at 24 weekly intervals.

Historical control data from 12 post-alemtuzumab treated subjects (Barts Health) for secondary endpoints (CSF OCB & FLC) and tertiary endpoints (B and T cell repertoires) will be used as comparators.

## 9. Study procedures

Participants will be counselled on the risks of the treatment and any study procedures (bloods, urine sampling and lumbar punctures) when obtaining full informed consent, and will specifically exclude those who may be vulnerable to these risks. Informed consent to participate in the study will be taken by the research fellow, treating neurologist or the study CI ([name]). It will be explained to all participants that they are free to withdraw their consent at any time without needing to provide an explanation, and their medical care will not be affected in any way if they decide not to participate. The data collected up to the point of withdrawal will be included in the analysis at the end.

All serious adverse events will be reported to the Sponsor and the research ethics committee by the project manager and PI (see Section 17: safety reporting). Clinical databases will be maintained by the project manager and access to personal data will be limited to the study team, and all other data will otherwise be anonymised. Day to day management of the study including MRI evaluation will be handled by the research fellow in conjunction with the neuroradiology department at Barts Health NHS Trust. Clinical scores, EDSS and timed 25 foot walk, and lumbar punctures will be performed by the research fellow or another trained neurologist listed on the delegation log.

Lumbar punctures will be performed using atraumatic needles to minimise the risk of post-puncture headaches at Barts Health NHS Trust day unit in accordance with routine clinical practice. Sample processing and storage (including freezer maintenance) will be performed by the laboratory technician in accordance with Departmental standard operating procedures (SOPs). Laboratory analysis will be performed by the research fellow, as well as the data analysis in conjunction with the study statistician.

Schedule of study interventions:

Week	Baseline prior to 1	Treatment Phase	Extra	Day 5	2	3	4	5	6	7	8	10	12	14	16	18	20	22	24	28	32	36	40	44	48	52	56	60	64	68	72	76	80	84	88	92	96
	Baseline - week 0																																				
Estimated Patient num	12	12		12	12	12	12	12	12	12	12	12	12	12	12	12	12	12	12	12	12	12	12	12	12	12	12	12	12	12	12	12	12				
Study specific visits				12	12	12	12	12	12	12	12	12	12	12	12	12	12	12	12	12	12	12	12	12	12	12	12	12	12	12	12	12	12				
Informed consent	1																																				
History	1																																				
Examination	1																																				
EDSS/MSFC/PROMS	1																																				
Oral Cladribine		1																																			
Labs																																					
FBC	1																																				
U&E	1																																				
LFTS	1																																				
TETs	1																																				
Pregnancy test	1																																				
HIV &2	1																																				
Hep B &C	1																																				
VarZV serology	1																																				
Syphilis serology	1																																				
-TB ellispot	1																																				
Procedures																																					
MRI	1																																				
LP	1																																				
Biobanking																																					
DNA	1																																				
Plasma	1	1	1	1	1	1	1	1	1	1	1	1	1	1	1	1	1	1	1	1	1	1	1	1	1	1	1	1	1	1	1	1	1	1			
Serum	1	1	1	1	1	1	1	1	1	1	1	1	1	1	1	1	1	1	1	1	1	1	1	1	1	1	1	1	1	1	1	1	1	1			
Cells	1	1	1	1	1	1	1	1	1	1	1	1	1	1	1	1	1	1	1	1	1	1	1	1	1	1	1	1	1	1	1	1	1	1			
CSF	1																																				
FAC & Biomarkers	1	1	1	1	1	1	1	1	1	1	1	1	1	1	1	1	1	1	1	1	1	1	1	1	1	1	1	1	1	1	1	1	1	1			
ImmunoSeq	1	1	1	1	1	1	1	1	1	1	1	1	1	1	1	1	1	1	1	1	1	1	1	1	1	1	1	1	1	1	1	1	1	1			
Urine	1																																				

Assumptions are based on a 6 month recruitment period  
 Routine NHS care  
 OCB-Specific Study care

